### 7.2 PARTICIPANT DISCONTINUATION/WITHDRAWAL FROM THE STUDY

N/A

### 7.3 LOST TO FOLLOW-UP

N/A

## 8 STUDY ASSESSMENTS AND PROCEDURES

*No text is to be entered in this section; rather it should be included under the relevant subheadings below.*

### 8.1 ENDPOINT AND OTHER NON-SAFETY ASSESSMENTS

*Participants receive task instructions, practice the task, and are allowed to ask questions prior to beginning the experimental block.*

### 8.2 SAFETY ASSESSMENTS

*Researchers monitor for any safety concerns (e.g. headaches), and participants are informed they may withdraw from the study at any time as part of our consent process.*

### 8.3 ADVERSE EVENTS AND SERIOUS ADVERSE EVENTS

#### 8.3.1 DEFINITION OF ADVERSE EVENTS

This protocol uses the definition of adverse event from 21 CFR 312.32 (a): any untoward medical occurrence associated with the use of an intervention in humans, ***whether or not considered intervention-related.***

#### 8.3.2 DEFINITION OF SERIOUS ADVERSE EVENTS

*Adverse events which go beyond typical daily occurrences.*

---

### 8.3.3 CLASSIFICATION OF AN ADVERSE EVENT

---

#### 1.1.1.1 SEVERITY OF EVENT

*All AEs will be assessed by the principal investigator. Any adverse events that go beyond typical events in daily life from computer use (e.g. headache) will be reported to Lehigh IRB.*

---

#### 1.1.1.2 RELATIONSHIP TO STUDY INTERVENTION/EXPERIMENTAL MANIPULATION

*Consultation with the Lehigh IRB will determine if the AEs are related or unrelated to the basic science intervention.*

---

#### 1.1.1.3 EXPECTEDNESS

*We expected events such as mild headache or boredom within our design, as these are typical for computer-based tasks. We did not expect any more serious adverse events. All researchers are told to report any potential adverse events to the PI.*

---

### 1.1.2 TIME PERIOD AND FREQUENCY FOR EVENT ASSESSMENT AND FOLLOW-UP

*Day of testing. If the PI has any concerns about an adverse event, she may directly reach out to the participant to obtain additional details or check on the participant.*

---

#### 1.1.3 ADVERSE EVENT REPORTING

*Adverse events are reported to Lehigh's IRB.*

---

#### 1.1.4 SERIOUS ADVERSE EVENT REPORTING

The PI will be responsible for conducting an evaluation of a serious adverse event and shall report the results of such evaluation to the NIH and the reviewing Institutional Review Board (IRB) as soon as possible, but in no event later than 10 working days after the investigator first learns of the event.

---

#### 1.1.5 REPORTING EVENTS TO PARTICIPANTS

*N/A*

---

#### 1.1.6 EVENTS OF SPECIAL INTEREST

N/A

---

#### 1.1.7 REPORTING OF PREGNANCY

N/A

### 1.2 UNANTICIPATED PROBLEMS

---

#### 1.2.1 DEFINITION OF UNANTICIPATED PROBLEMS

- *We experience unanticipated computer issues (e.g. code not working, file not saving) occasionally.*

---

#### 1.2.2 UNANTICIPATED PROBLEMS REPORTING

The PI will report unanticipated problems (UPs) that are deemed significant (e.g. not the expected unanticipated issues listed above) to the reviewing Institutional Review Board (IRB). The UP report will include the following information:

- Protocol identifying information: protocol title and number, PI's name, and the IRB project number
- A detailed description of the event, incident, experience, or outcome
- An explanation of the basis for determining that the event, incident, experience, or outcome represents an UP
- A description of any changes to the protocol or other corrective actions that have been taken or are proposed in response to the UP

See [CD Section 8.4.1](#) for additional example text applicable for devices.

---

#### 1.2.3 REPORTING UNANTICIPATED PROBLEMS TO PARTICIPANTS

N/A

## 2 STATISTICAL CONSIDERATIONS

### 2.1 STATISTICAL HYPOTHESES

If the negative template requires the general inhibition of the oculomotor system to reduce the likelihood of the prepotent response, we expect to find a unidirectional switch cost (e.g. a switch cost for positive cues which is not present for negative cues).

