### 2.2 BACKGROUND

Previous research has shown that, when there are no competing task demands, attention is likely to be directed to items in the visual field that match working memory (Downing, 2000). This suggests that the prepotent response is to attend to memory-matching items, whereas to utilize a negative cue one must actively avoid attending the memory-matching items. This is a good example of how higher-order cognitive control can be used to inhibit prepotent responses. A similar example from oculomotor control is the anti-saccade task. In this task, participants must either make a pro-saccade toward a cue or an anti-saccade away from the cue, depending on the identity of the cue. A unidirectional switch cost has been shown within the anti-saccade task when participants must engage in task switching between pro- and

anti-saccades (Weiler & Heath, 2012). When participants switch from an anti-saccade task to a pro-saccade task, there is a typical switch cost as compared to pro-saccade repetition. However, the opposite pattern is found for anti-saccades- participants are either faster to perform an anti-saccade after a prosaccade (task switch) compared to an anti-saccade repetition (Barton, et. al, 2002) or show no task switch effect (Weiler & Heath, 2012). This is thought to reflect a residual inhibition of the pre-potent response following an anti-saccade. This slows a subsequent pro-saccade, but can also slow an anti-saccade as well. Therefore, the unidirectional switch cost is a hallmark of inhibition within the oculomotor system.

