## 3 OBJECTIVES AND ENDPOINTS

OBJECTIVES	ENDPOINTS	JUSTIFICATION FOR ENDPOINTS	PUTATIVE MECHANISMS OF ACTION

Primary
 
Compare Task-Switching Costs for Positive Target Cues and Negative Distractor Cues
	Reaction Time Accuracy	Cognitive Function	Conflict in Cognitive Control leads to task-switching costs

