### 4.1 OVERALL DESIGN

Hypothesis: If the negative template requires the general inhibition of the oculomotor system to reduce the likelihood of the prepotent response, we expect to find a unidirectional switch cost. Within-Subjects, single arm design, single site.

Visual Search Information Type (target or distractor information) Participants will have information about targets or distractors via cues before a visual search trials, in different trials of the intervention.

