## 6 STUDY INTERVENTION(S) OR EXPERIMENTAL MANIPULATION(S)

## 6.1 STUDY INTERVENTION(S) OR EXPERIMENTAL MANIPULATION(S) ADMINISTRATION

### 6.1.1 STUDY INTERVENTION OR EXPERIMENTAL MANIPULATION DESCRIPTION

Participants will receive one of three types of visual cues before performing a visual search task. Positive cues for visual search (cues to enhance), or negative cues for visual search (cues to suppress). After subjects receive the color cue for a trial, they will perform a visual search task for a shape-defined target (landolt-C). We will examine task switching costs for changes in the color of the cue, changes in the meaning of the cue, neither or both. We will measure 'task-switching costs' by contrasting reaction times when an aspect of the trial changes compared to when neither aspect of the trial changes compared to the previous trials. We will collect behavioral results using Matlab and a computer.

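### A switch cost confined to positive cues, measured by reaction time and accuracy, cannot be attributed specifically to the oculomotor system, and requiring no cost for negative cues can miss a real after-effect

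*Combined protocol and SAP*

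**What the plan says.** Overall Design and Statistical Hypotheses share one conditional statement: "If the negative template requires the general inhibition of the oculomotor system to reduce the likelihood of the prepotent response, we expect to find a" one-way (unidirectional) switch cost. Statistical Hypotheses illustrates this as "a switch cost for positive cues which is not present for negative cues".

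The endpoints under Objectives and Endpoints are "Reaction Time Accuracy", and the same table gives the putative mechanism as "Conflict in Cognitive Control leads to task-switching costs". The intervention description adds "We will collect behavioral results using Matlab and a computer". The Schedule of Activities lists visual search performance as the only outcome. No section plans an eye-movement measure.

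The link between the behavioural pattern and the oculomotor system is in Background. Drawing on work with pro- and anti-saccades, it treats a one-way switch cost as a hallmark of oculomotor inhibition and explains it by inhibition left over from an anti-saccade: "This slows a subsequent pro-saccade, but can also slow an anti-saccade as well".

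The primary analysis is an ANOVA of Cue Meaning, Cue Meaning Repetition and Cue Color Repetition, run on each endpoint.

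**The concern.** There are two separate difficulties.

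- **Attribution.** In the saccade studies the response is itself an eye movement. Here the response is a visual search judgement, scored by speed and accuracy. Inhibition at a more general level of cognitive control could produce the same pattern, and the plan does not argue why the saccade hallmark carries over.
- **Criterion.** By the account in Background, residual inhibition can slow whatever follows a negative trial, including another negative trial. Whether the negative cue then shows no switch cost depends on the size of the ordinary switch cost as well as on the inhibition.

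At stake is the trial's main conclusion. A non-significant negative cost could be reported as oculomotor inhibition that nobody measured. A real after-effect could be dismissed because some cost remained for negative cues.

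**Working it through.** **The plan's own figure.** The documents give no expected switch cost. The only related figure is the sample size: f = 0.2, 8 measurements, correlation 0.5, ε = 1, N = 24. Then λ = 0.2² × 24 × 8 / (1 − 0.5) = 15.36, with 7 and 23 × 7 = 161 degrees of freedom, critical F = 2.0669 and power 0.8116. This reproduces the plan. It is the power of a 7-df test and gives no power for one cue's cost or for the difference between the costs.

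**Cell algebra.** Let P and N be the current cue (positive, negative) and p and n the cue on the preceding trial. Switch cost is switch RT minus repeat RT, following Study Rationale, averaged over color repetition.

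- Positive cost = RT(P after n) − RT(P after p).
- Negative cost = RT(N after p) − RT(N after n).

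The cells RT(P after n) and RT(N after n) both follow a negative trial. Let C be the ordinary cost of any change of meaning and d the slowing after a negative trial:

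- Positive cost = C + d.
- Negative cost = C − d, because d slows the repeat trial that is subtracted.
- Difference = (C + d) − (C − d) = 2d.

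The negative cost is zero or reversed only if C ≤ d.

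**Illustration (C and d are assumed, in ms).**

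| C | d | Positive cost | Negative cost | Fits the stated pattern? | Difference |
|---|---|---|---|---|---|
| 50 | 20 | 70 | 30 | No | 40 |
| 20 | 20 | 40 | 0 | Yes | 40 |
| 0 | 20 | 20 | −20 | Yes (reversed) | 40 |

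The after-effect is the same in every row. Fit to the stated pattern changes with C, and the difference does not.

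**Without the additive model.** Rearranging the cells, the difference equals [RT(P after n) + RT(N after n)] − [RT(P after p) + RT(N after p)]. So the Cue Meaning × Cue Meaning Repetition interaction is, as an identity, the contrast of trials after a negative cue with trials after a positive cue. Reading it as 2d requires the same C for both cues. With separate values C_P and C_N it equals 2d + (C_P − C_N).

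**Can a non-significant negative cost show absence?** The plan sets no equivalence margin. For a two-sided paired test at 0.05 with N = 24, over assumed standardised costs:

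| Standardised cost | Power | Chance of missing it |
|---|---|---|
| 0.3 | 0.29 | 0.71 |
| 0.4 | 0.47 | 0.53 |
| 0.5 | 0.65 | 0.35 |
| 0.6 | 0.80 | 0.20 |
| 0.8 | 0.96 | 0.04 |

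A real cost of 0.4 would be missed about half the time. The same powers apply to a test of the difference between the costs.

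**The case against.** The best defence is that the planned analysis already isolates the right quantity. The objective is to compare the costs for the two cue types, and the interaction that does so is in the primary ANOVA. No rule in the plan says that a non-zero negative cost means no inhibition, and the pattern in Statistical Hypotheses is introduced only as an example. This stands as far as the data and the ANOVA go. But the plan does not name that interaction as the test of the hypothesis, and the only operational form it gives is an absent negative cost.

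Background does supply a bridge from behaviour to mechanism, and it places negative cueing and anti-saccades together as cases of controlled inhibition. That makes the oculomotor reading a reasonable conjecture. It does not make it something that reaction time and accuracy can establish.

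A reader might go further than the documents allow in four ways:

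- **That the hypothesis is untestable.** It is a conditional statement, so clear equal costs, or a larger cost for negative cues, would count against it. Confirmation of the oculomotor claim is the weak side.
- **That an absent negative cost needs C to equal d by coincidence.** Any C at or below d will do. Background reports both faster switches and no switch effect for anti-saccades, so a reversed cost fits too.
- **That the conflict mechanism is a rival account predicting costs for both cues.** Objectives and Endpoints makes no cue-specific prediction. The two wordings are unreconciled, but they are not shown to conflict.
- **That responses are button presses.** No response device is named.

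**Conclusion.** The point holds as one of interpretation. Reaction time and accuracy cannot attribute a unidirectional cost specifically to oculomotor inhibition. The stated pattern also fails a real after-effect whenever C exceeds d, while the difference of the costs equals 2d for any common C. The size of the problem in this trial cannot be given, because the documents contain no values for C or d; the millisecond and standardised figures above are assumptions.

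The algebra rests on two cue meanings, as in the ANOVA. The intervention description speaks of three cue types but names only two. It also takes C and d to be the same for both current cues. If C differs by cue, the interaction still measures the overall contrast between trials after negative and after positive cues, but its source is less certain, which is a further reason for a modest conclusion. Sample size, data collection and the validity of the ANOVA are not affected.

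**What to change.** - **Overall Design and Statistical Hypotheses:** state the primary prediction as a larger meaning-switch cost in reaction time for positive than for negative cues, and name the Cue Meaning × Cue Meaning Repetition interaction in the existing ANOVA as its test.
- **Analysis of the Primary Endpoint(s):** report each cue's switch cost, and their difference, with a confidence interval. Say that a non-significant negative cost will not be read as absence, nor a non-significant difference as equality.
- **Conclusions:** limit them to an after-effect of negative cues on attentional control, with oculomotor inhibition as a possible interpretation only.
- **Objectives and Endpoints:** bring the mechanism entry into line with the restated hypothesis.

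The cost is a few sentences and a narrower claim. Data collection and the ANOVA do not change.

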## 2.2 SAMPLE SIZE DETERMINATION

**GPower analysis: Repeated measures ANOVA with 8 factors (4 different trial types x 2 cue types, positive vs. negative cues)**

**F tests** - ANOVA: Repeated measures, within factors

**Analysis:** A priori: Compute required sample size

**Input:** Effect size f = 0.2

α err prob = 0.05

Power (1-β err prob) = 0.8

Number of groups = 1

Number of measurements = 8

Corr among rep measures = 0.5

Nonsphericity correction ε = 1

**Output:** Noncentrality parameter λ = 15.3600000

Critical F = 2.0668747

Numerator df = 7.0000000

Denominator df = 161

Total sample size = 24

Actual power = 0.8115711

We will recruit 24 participants to meet the required sample size.

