## 2 INTRODUCTION

### 2.1 STUDY RATIONALE

The PI provided the first evidence that attentional control can also be used to ignore known distractor features (Arita, [name], & Woodman, 2012). In this study, participants received a cue before each trial of a visual search task where they searched for a shape-defined target (a gap-up or gap-down Landolt-c) and reported the location of the gap. The cue could be a positive cue (indicating the target would appear in that color in the upcoming array), a negative cue (indicating the target *would not* appear in that color in the upcoming array), or a neutral cue (the cued color did not appear in the upcoming array). These cue meanings were manipulated across blocks. Importantly, because only two colors appeared in the search array, the positive and negative cues had the same information value. If participants used the cue, they could reduce the number of items they needed to search to find the target by half. We found participants can use visual attentional control to actively ignore items based on a feature cue, as indicated by reaction time (RT) benefits for the negative cued condition compared to the neutral condition.

In this study, participants will receive a cue on each trial that indicates a feature (e.g. red) and the cue meaning (positive + or negative -). Across trials, we will be able to independently alter the feature template and the cue meaning (Figure 5A). This will allow us to ensure the results are driven by shifts in the cue meaning, and not simply alterations to the color that is cued. This will lead to trials where both the feature and the meaning repeat (RE-repeat trials), trials where only the cue feature changes (CC-color change, meaning repeat), trials where only the cue meaning changes but the color repeats (MC-meaning change, color repeat), and trials where both feature and cue meaning change (BC-both change). To look for task switching costs, we will subtract the reaction times for repeat trials from each type of switch trials. Importantly, the visual search is defined by a shape-defined target across all trials, meaning that there should be no cross talk or response interference that could interfere with our ability to measure task-switching costs (Koch, Poljac, Müller, & Kiesel, 2018).

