#### 2.4.2 ANALYSIS OF THE PRIMARY ENDPOINT(S)

For both Reaction time and Accuracy, we will perform an ANOVA with these factors: Cue Meaning (Target Color Positive Cue or Distractor Color Negative Cue) x Cue Meaning Repetition (Repeat, Non-Repeat) X Cue Color Repetition (Repeat, Non-Repeat) Repetition.

---

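### N=24 and power 0.81 hold only for a 7-df omnibus test that is not among the planned analyses; the plan neither designates the contrast that tests the switch-cost hypothesis nor gives its power

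*Combined protocol and SAP*

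**What the plan says.** Section 2.2 (Sample Size Determination) describes the model as "Repeated measures ANOVA with 8 factors (4 different trial types x 2 cue types, positive vs. negative cues". It enters f=0.2, alpha 0.05, eight measurements, correlation 0.5 and no sphericity correction. The output has 7 and 161 degrees of freedom and "Actual power = 0.8115711", and the section concludes: "We will recruit 24 participants to meet the required sample size".

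Section 2.4.2 plans, for both reaction time and accuracy, an ANOVA that crosses cue meaning (positive or negative) with "Cue Meaning Repetition (Repeat, Non-Repeat) X Cue Color Repetition (Repeat, Non-Repeat". It singles out no effect.

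The question itself is stated in two places. The primary objective in section 3 is "Compare Task-Switching Costs for Positive Target Cues and Negative Distractor Cues". The statistical hypothesis (section 2.1, Statistical Hypotheses) is "a switch cost for positive cues which is not present for negative cues".

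Switch cost is defined on reaction time. The Study Rationale says "we will subtract the reaction times for repeat trials from each type of switch trials", where the switch types are colour change (CC), meaning change (MC) and both change (BC). Section 6.1.1 likewise speaks of "contrasting reaction times when an aspect of the trial changes compared to when neither aspect of the trial changes".

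**The concern.** The calculation treats the eight cells as one 8-level factor. A rejection on 7 df says only that some cell mean differs from another. It could come wholly from main effects, such as slower search after negative cues or after a colour change, with no difference in switch cost between cue types. Power for that test therefore does not carry over to the study's question.

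N=24 rests entirely on this block. As the plan stands, a reader cannot tell which contrast will decide the hypothesis or how large a difference in switch cost 24 participants can detect.

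**Working it through.** **Inputs.** From section 2.2: f=0.2, m=8, rho=0.5, epsilon=1, N=24, alpha 0.05. From section 2.4.2: three within-subject factors with two levels each.

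**1. The plan's own figure.**
- lambda = f² × N × m / (1 − rho) = 0.04 × 24 × 8 / 0.5 = 15.36.
- df = 7 and 23 × 7 = 161; critical F = 2.0669.
- Power = 0.8116 at N=24 and 0.7905 at N=23, so 24 is the minimum. All stated figures reproduce.

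**2. What the planned ANOVA tests.** A 2x2x2 design splits the 7 df into seven effects of 1 df each (three main effects, three two-way interactions, one three-way interaction). For each effect the error df is N − 1 = 23 and critical F is 4.279. No 7-df test is listed. The effect closest to the hypothesis is Cue Meaning × Cue Meaning Repetition, which averages over colour repetition. That identification is an inference, because the plan names no key effect.

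**3. Power of that interaction at N=24, by what f=0.2 is taken to mean.** Here dz is the mean of the within-person contrast divided by its SD, and lambda = N × dz².

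| Reading of f=0.2 | lambda | dz | Power, F(1,23) |
|---|---|---|---|
| Spread evenly over the 7 df | 15.36/7 = 2.19 | 0.30 | 0.29 |
| Entered for a two-measurement contrast | 0.04 × 24 × 2/0.5 = 3.84 | 0.40 | 0.47 |
| Only the two positive/non-repeat cells raised | 15.36/3 = 5.12 | 0.46 | 0.58 |
| All of lambda in this interaction | 15.36 | 0.80 | 0.96 |

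In the third row, raising two of eight cells splits lambda equally between two main effects and their interaction, hence the factor 1/3.

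The description of four trial types by two cue types could instead suggest a 3-df trial type × cue interaction, F(3,69). Its power is 0.43 for the cell pattern of the third row (lambda 5.12) and 0.91 if all of lambda lies in it. That is not 0.81 either.

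**4. A statement that does not depend on f.** For a 1-df contrast at two-sided alpha 0.05, 80% power at N=24 needs lambda = 8.559, so dz = √(8.559/24) = 0.597. With 22 analysed (assuming two exclusions under the accuracy rule in section 2.3) it is 0.626. With 27 (the synopsis figure) it is 0.560.

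**5. In cell-SD units, at rho=0.5.** The variance of a contrast is (1 − rho) × the sum of squared coefficients.
- Colour-averaged interaction: eight coefficients of ±½, variance 0.5 × 2 = 1, SD 1.000. The detectable difference in cost is 0.597 × 1.000, about 0.60 cell SD.
- MC minus full-repeat, positive minus negative: four coefficients of ±1, variance 0.5 × 4 = 2, SD 1.414. The detectable difference is 0.597 × 1.414, about 0.84 cell SD.

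The choice of contrast therefore changes what 24 participants can detect.

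**The case against.** The strongest reply is that nothing is missing from the model. The section 2.4.2 ANOVA is a full factorial, so it contains the interaction, and the Study Rationale explains that colour and meaning are varied independently so that an effect can be attributed to cue meaning. That stands: the test is present. What is absent is its designation as the key test and a power figure for it.

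A second reply is that N=24 may be ample. That also stands as a possibility. If f=0.2 is the interaction's own effect, power is 0.96. Even under the pattern that gives 0.58 for the interaction, the positive-cue cost averaged over colour has lambda 10.24 and power 0.87.

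A reader might infer that the study is underpowered, or that the power calculation is wrong. The documents support neither. Every number in section 2.2 is correct for the test it describes, and because the meaning of f=0.2 is not given, power for the hypothesis may be above or below 0.81.

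Nor can the review choose the contrast. The colour-averaged interaction fits section 2.4.2. The definitions in the Study Rationale and section 6.1.1 take full-repeat trials as reference, and the Rationale applies this to CC, MC and BC, not to MC alone. Only the sponsor can say which is meant.

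**Conclusion.** The point holds as a mismatch between the sample-size calculation and the planned analysis. The 0.81 is correct for F(7,161) and is not the power of any effect in the planned ANOVA. Power for the colour-averaged interaction at N=24 lies between 0.29 and 0.96 over the four readings examined. It reaches 80% when dz is about 0.60, that is, when about 56% of the stated lambda (8.559/15.36) lies in that contrast. These figures assume the plan's correlation of 0.5 wherever f or cell SDs are used; the dz values do not depend on it. It is a gap in the only justification given for N, and it should be corrected. It is not evidence of inadequate power and does not by itself call for more participants.

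**What to change.** Amend sections 2.2 and 2.4.2 as follows.

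1. **Designate the test.** The sponsor names the reaction-time contrast that tests the hypothesis: either the colour-averaged Cue Meaning × Cue Meaning Repetition interaction, or the contrast that matches the cost against full-repeat trials, stating which of CC, MC and BC it uses. The choice is made without sight of outcome data, or else labelled post hoc. This matters because the synopsis already gives a count by sex and section 6.4 is in the past tense, so data may exist, although the documents do not establish this. Accuracy remains a listed endpoint.
2. **Report both costs.** Give the switch cost with a 95% CI separately for positive and negative cues. An interaction alone does not show a cost in one cue type and none in the other, and a non-significant negative-cue cost must not be read as absence.
3. **Restate the power.** Label 0.81 as the power of the 7-df omnibus test only. Add, for example: *With 24 analysed participants and two-sided alpha 0.05, a 1-df contrast has 80% power for dz of about 0.60 (0.63 if 22 are analysed, 0.56 if 27).* Give the cell-SD equivalent at correlation 0.5 for the chosen contrast: about 0.60 if colour-averaged, about 0.84 for MC minus full-repeat.

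The cost is a rewrite of section 2.2, a short addition to 2.4.2, and a less favourable-looking statement than a single 0.81.
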